3.2. Study Design

This protocol describes a randomized, double-blind comparison of the safety and efficacy of F/TAF versus F/TDF administered once daily for at least 96 weeks in HIV-1–negative adult MSM or TGW (male at birth) who have sex with men and are at risk of HIV-1 infection.

All participants must meet all eligibility criteria in order to receive treatment in the study. Once randomized to receive treatment in the study, all participants must return to the study center for required visits at Weeks 4, 12, and every 12 weeks thereafter.

All participants will remain blinded to study drug for at least 96 weeks. The primary endpoint data will be collected and analyzed when all participants have a minimum follow up of 48 weeks and 50% of the participants have 96 weeks of follow up after randomization.

Once all participants have at least 96 weeks of follow up after randomization and upon notification by Gilead, all participants will return to the study center for an end of blinded treatment phase visit (may coincide with their next scheduled visit).

Participants who are still on blinded study drug at the end of blinded treatment phase visit will be offered entry into the OL phase of the study. CCI

Participants who have discontinued study drug prior to the end of blinded treatment phase visit due to HIV infection will be eligible to continue participation in the OL phase up to OL Week 48, but will not be administered F/TAF once daily. From OL Week 48 participants who acquire HIV must complete the early study drug discontinuation (ESDD) visit and discontinue the study at the 30-Day Follow-up visit, 30 days after the last dose of study drug. Participants who have discontinued study drug for any other reason prior to the end of blinded treatment phase visit will not be eligible to participate in the OL phase.

[figure not shown]
CCI

During the blinded treatment phase, participants may choose to continue to participate in the study without taking study drug (“on-study, off-study drug”). Participants who permanently discontinue study drug and continue to attend normal study visits (at minimum one visit at least 30 days after last dose) are not required to complete the follow-up visit. Any participant who has an ESDD visit and who will not continue participating in the study, or any participant who will not continue participation in the OL phase of the study, must complete the 30-Day Follow-Up visit 30 days after the last dose of study drug.

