6. STUDY PROCEDURES

The study procedures to be conducted for each participant enrolled in the study are presented in tabular form in [Appendix 2](#) and [Appendix 3](#) and described in the text that follows. The investigator must document any deviation from protocol procedures and notify the sponsor or contract research organization (CRO).

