6.4. End of Blinded Treatment Phase Visit

Once all participants have had at least 96 weeks of follow up after randomization and upon notification by Gilead, all participants will return to the study center for an end of blinded treatment phase visit (may coincide with their next scheduled study visit).

Participants who do not participate in the OL phase will discontinue their blinded study drug and will return for a 30-Day Follow-Up visit following the end of blinded treatment phase visit.

The following will be performed at the end of blinded treatment phase visit:

- Targeted (symptom directed) physical examination
- Review of AEs and changes in concomitant medications, including assessment of whether any STIs were diagnosed and any treatments were received since the last visit
- When clinically indicated, vital signs measurement (blood pressure, pulse, respiration rate, and temperature)
- Weight
- STI testing. Participants who test positive for any STI will be treated in accordance with local STI guidelines.
 - Genital, rectal, and pharyngeal examination as appropriate
 - Pharyngeal and rectal swabs for gonorrhea and chlamydia (per local lab). Swabs may be self-administered by the participant at the discretion of the investigator.
 - Urine sample for gonorrhea and chlamydia (per central lab)
 - Blood sample for syphilis testing (per local lab)
- Fourth generation rapid HIV-1 Ag/Ab or third generation rapid HIV-1 Ab test (**not done for participants who acquire HIV**)
 - If the result for rapid testing is positive, a retest will be completed. If the retest is positive, an HIV-1 RNA by PCR test and sample collection for possible genotypic resistance testing will be completed.

- Urine collection for urinalysis, urine proteins, urine chemistry (uric acid, phosphate, and creatinine), and sample storage
- Blood sample collection for the following central laboratory analyses:
 - Hematology profile: CBC with differential and platelet count
 - Chemistry profile: alkaline phosphatase, AST, ALT, GGT, total bilirubin, direct and indirect bilirubin, total protein, albumin, LDH, bicarbonate, BUN, calcium, chloride, creatinine, glucose, phosphorus, magnesium, potassium, sodium, uric acid, and amylase (reflex lipase testing is performed in participants with total amylase $> 1.5 \times$ ULN)
 - Estimated GFR according to the Cockcroft-Gault formula for creatinine clearance
 - HIV-1 Ab/Ag (not done for participants who acquire HIV)

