6.5. Treatment Assessments Open-Label Phase and Open-Label Extension Phase

All study visits in the OL phase and OL extension phase are to be scheduled relative to the end of blinded treatment phase visit date. Study visits are to be completed within ± 14 days of the protocol-specified visit date based on the end of blinded treatment phase visit. Participants participating in the OL phase and OL extension phase will return for study visits every 12 weeks.

From OL Week 48, participants who acquire HIV must complete the ESDD visit and discontinue the study at the 30-Day Follow-up visit, 30 days after the last dose of study drug.

CCI [REDACTED]

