For details regarding confirmation of HIV infection, please refer to Section [6.11](#).

— CD4, CD8, and CD4/CD8 ratio (for participants that acquire **HIV**)

- Collect and review used and unused study drug for accountability and calculate compliance

At the ESDD visit, any evaluations showing abnormal results that the investigator determines to have a possible or probable causal relationship with the study drug, will be repeated weekly (or as often as deemed prudent by the investigator) until the abnormality is resolved, returns to baseline, or is otherwise explained.

6.7.3. 30-Day Follow-Up Assessment

All participants who have received at least one dose of study drug will be required to complete a follow-up visit 30 days (+ 14 days) after discontinuation of the study drug. Participants who permanently discontinue study drug and continue to attend normal study visits (at minimum one visit at least 30 days after last dose) are not required to complete the follow-up visit.

At the 30-Day Follow-Up visit, **any evaluations showing abnormal results that the investigator determines to have a possible or probable causal relationship with the study drug will be repeated weekly (or as often as deemed prudent by the investigator) until the abnormality is resolved, returns to baseline, or is otherwise explained.**

The following evaluations are to be completed at the 30-Day Follow-Up visit (**Prior to OL Week 96**):

- Targeted (symptom directed) physical examination
- Review of AEs and changes in concomitant medications, including assessment of whether any STIs were diagnosed and any treatments were received since last visit

- When clinically indicated, vital signs measurement (blood pressure, pulse, respiration rate, and temperature)
- Weight
- STI testing. Participants who test positive for any STI will be treated in accordance with local STI guidelines.
 - Genital, rectal, and pharyngeal examination as appropriate
 - Pharyngeal and rectal swabs for gonorrhea and chlamydia (per local lab). Swabs may be self-administered by the participant at the discretion of the investigator.
 - Urine sample for gonorrhea and chlamydia (per central lab)
 - Blood sample for syphilis testing (per local lab)
- Fourth generation rapid HIV-1 Ab/Ag or third generation rapid HIV-1 Ab test (**not done for participants who acquire HIV**)

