- a All study visits in the double-blind phase are to be scheduled relative to the Day 1 visit date. Visit windows are ± 2 days of the protocol-specified date through Week 12, ± 14 days of the protocol-specified date through the end of blinded treatment phase visit, unless otherwise specified.
- b end of blinded treatment phase visit to occur after all participants reach Week 96.
- c Study visits are to be completed within ± 14 days of the protocol-specified visit date based on the end of blinded treatment phase visit.
- d Participants will continue study visits every 12 weeks in the OL phase up to OL Week 96 (not including OL Week 96). From OL Week 96, refer to [Appendix 3](#).

- e For 30-Day Follow-up visits conducted prior to OL Week 96, must be completed 30 days after discontinuing study drug. All participants who have received at least one dose of study drug will be required to complete a follow-up visit. For the purpose of scheduling a 30-Day Follow-Up visit, a ± 14 days window may be used.
- f For Early Study Drug Discontinuation Visits conducted prior to OL Week 96, visit to occur within 72 hours of last dose of study drug. Participants will be asked to continue attending the scheduled study visits through the end of blinded treatment phase visit.
- g Vital signs measurement including blood pressure, pulse, respiration rate, and temperature. After the Day 1 visit, vital signs completed when clinically indicated.
- h Chemistry profile: alkaline phosphatase, AST, ALT, GGT, total bilirubin, direct and indirect bilirubin, total protein, albumin, LDH, bicarbonate, BUN, calcium, chloride, creatinine, glucose, phosphorus, magnesium, potassium, sodium, uric acid, and amylase (reflex lipase testing is performed in participants with total amylase $> 1.5 \times$ ULN).
- i Complete blood count (CBC) with differential and platelet count
- j [REDACTED]
- k Local STI testing for syphilis.
- l [REDACTED]
- m For possible PK, virology, and/or safety testing
- n Computer-assisted self-interview (CASI)
- o If Day 1 is completed > 7 days after the screening visit

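### The protocol gives two windows for the 30-Day Follow-Up visit: Days 30-44 in Section 6.7.3 and Days 16-44 in the Appendix 2 and 3 footnotes, which let a leaver's last scheduled contact fall up to 14 days before AE reporting ends

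*Protocol*

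**What the plan says.** Section 6.7.3 requires everyone who has taken study drug to "complete a follow-up visit 30 days (+ 14 days) after discontinuation of the study drug". A participant who stops drug but stays on study is excused only if there is "at minimum one visit at least 30 days after last dose".

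Appendix 2 footnote e (before OL Week 96) and Appendix 3 footnote c (from OL Week 96) first call for the visit 30 days after stopping. Both then add: "For the purpose of scheduling a 30-Day Follow-Up visit, a ± 14 days window may be used".

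Other sections show who depends on this visit:
- Section 3.2: anyone leaving after an early discontinuation visit, or not going on to the OL phase, "must complete the 30-Day Follow-Up visit 30 days after the last dose of study drug". No window is given there.
- Section 6.4: "Participants who do not participate in the OL phase will discontinue their blinded study drug and will return for a 30-Day Follow-Up visit".
- Section 6.5: from OL Week 48, participants who acquire HIV must "discontinue the study at the 30-Day Follow-up visit, 30 days after the last dose of study drug".

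Section 7.3.2 requires all AEs to be reported until 30 days after the last dose. Section 8.5.2 counts events with onset up to 30 days after the stop date as treatment-emergent.

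**The concern.** The body text and the tables disagree on when a required safety visit takes place. Sites often schedule from the tables.

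A visit on Days 16-29 complies with the footnotes but is too early under Section 6.7.3. Section 6 says "The investigator must document any deviation from protocol procedures and notify the sponsor or contract research organization", so two sites could classify the same visit differently.

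The safety issue is ascertainment at the end of the AE period. For a leaver seen on Day 16, no later scheduled contact asks about events on Days 17-30. Those events must still be reported and would count as treatment-emergent. A new non-serious AE in that interval reaches the database only if the participant volunteers it or the site learns of it some other way.

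**Working it through.** No power, alpha or sample size figure is involved. The check is window arithmetic. Section 6.7.3 counts from discontinuation and Section 7.3.2 from last administration; these are treated as the same day.

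| Source | Rule | Earliest day | Latest day |
|---|---|---|---|
| Section 6.7.3 | 30 days, + 14 | 30 | 30 + 14 = 44 |
| Appendix 2 footnote e | 30 days, ± 14 | 30 − 14 = 16 | 30 + 14 = 44 |
| Appendix 3 footnote c | 30 days, ± 14 | 30 − 14 = 16 | 30 + 14 = 44 |

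The AE period ends on Day 30 (Sections 7.3.2 and 8.5.2).

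1. Largest gap between the last scheduled contact and the end of the AE period, under the footnotes: 30 − 16 = 14 days.
2. The same gap under Section 6.7.3: 30 − 30 = 0 days.
3. Days allowed by the footnotes but not by Section 6.7.3: Days 16-29, which is 29 − 16 + 1 = 14 possible visit days.
4. Days allowed by all three: Days 30-44. Aligning the footnotes to Section 6.7.3 adds no new visit day and leaves a largest gap of 0.

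What the gap leaves open, by type of event:
- **SAEs and deaths:** Section 7.3.3 asks for those occurring after the follow-up visit but within 30 days of the last dose, so the reporting rule covers them.
- **Non-serious AEs:** Section 7.3.2 makes them reportable to Day 30, but no scheduled contact after an early visit elicits new ones.
- **HIV endpoint:** SAP Section 6.2.3 ends an uninfected participant's person-time at the last HIV test, so an early visit does not add untested follow-up time.

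The conflict turns on one character in Section 6.7.3, as read from the PDF. Two things make a misread unlikely. The ± sign is rendered correctly in the same body text in Section 6.5 ("Study visits are to be completed within ± 14 days of the protocol-specified visit date"). The waiver in Section 6.7.3 also independently asks for a visit at Day 30 or later. If the + were nevertheless a slip for ±, the wording conflict would disappear, but the 14-day gap would then exist under every wording.

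**The case against.** The strongest counter-argument comes from Section 7.3.3. Its provision for SAEs and deaths after the follow-up visit but within 30 days would have almost no content if the visit could never precede Day 30. It reads as though early visits were foreseen, which fits ±. The ± wording stands in both protocol tables and + only once. The waiver governs when a routine visit may replace the follow-up visit; strictly, it does not set that visit's window. This stands in part: the documents do not prove that + was always intended. It does not remove the conflict, and it does not justify accepting Day 16 for those who leave when those who stay need a visit at Day 30 or later.

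A second argument is that the consequence is thin. Reporting to Day 30 is required whenever the visit falls. Section 6.7.3 repeats abnormal findings thought possibly or probably drug-related until they resolve or are explained, so an early visit is not always the last contact. Blinded-phase participants who stop drug are encouraged to stay in follow-up (Section 6.9). All of this stands and limits the point to new non-serious AEs in leavers.

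A reader might go further and infer a biased efficacy result or safety comparison. The documents do not support that. The window is the same in both arms, person-time stops at the last HIV test, and no count of early visits is given.

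Nor do the documents show that the conflict existed during the blinded phase. SAP Section 1 rests on protocol amendment 5, and that version's Section 6.7.3 is not available.

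**Conclusion.** The inconsistency is real and sits in current protocol text. It is minor. The footnotes allow a last scheduled contact up to 14 days before the AE period ends; Section 6.7.3 allows none. Fourteen days is a worst-case bound for one participant seen on Day 16, not an estimate of typical loss. The number seen on Days 16-29 is not in the documents.

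The exposure is incomplete elicitation of new non-serious AEs among leavers, together with uncertainty over whether a Day 16-29 visit is a protocol deviation. This rests on reading the + in Section 6.7.3 as printed and on treating discontinuation and last dose as the same day.

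A reader might also infer that the SAP needs correcting, because footnote e of the table in SAP Appendix 1 carries ± as well. That does not follow. The SAP is based on amendment 5, and its table still holds open-label rules that the current protocol has dropped. Treatment-emergent AEs are classified by onset date (SAP Section 7.1.5.1), so the footnote drives no analysis.

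**What to change.** In Protocol Appendix 2 footnote e and Appendix 3 footnote c, change ± 14 days to + 14 days. All three places then give Days 30-44, the window that reaches the end of the AE period and agrees with the Day-30 condition in the waiver. Leave SAP Appendix 1 unchanged.

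The cost is two footnote edits and no new procedure. There is one small downside. Follow-up laboratory samples that would have been drawn on Days 16-29 may move past Day 30, where Section 8.5.3 puts abnormalities in a listing rather than in the treatment-emergent summary. How many is unknown. Section 6.7.3 already requires that timing, and samples on Days 31-44 are handled the same way under either wording.

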Appendix 3. Study Procedures Table (OL Week 96 and beyond)

[figure not shown]
Study Procedure	Open-Label Extension Treatment End of Week ^a		
	OL Week 96 and Every 12 Weeks until OL Week 408 ^b	30-Day Follow-up ^c	ESDD ^d
Concomitant Medications	X	X	X
Adverse Events	X	X	X
Targeted Physical Exam ^f	X ^f	X	X
Vital Signs ^e	X ^e	X	X
Weight ^f	X ^f	X	X
Genital, Rectal, and Pharyngeal Examination for STIs as appropriate	X	X	X
Pharyngeal Swab for Gonorrhea and Chlamydia (Local Laboratory) ^g	X	X	X
Rectal Swab for Gonorrhea and Chlamydia (Local Laboratory) ^g	X	X	X
Urine Sample for Gonorrhea and Chlamydia	X	X	X
Rapid HIV-1 Ag/Ab Test (In-Clinic) ^h	X	X	X
HIV-1 Ab/Ag ⁱ	X	X	X
HIV-1 RNA by PCR ^j	X	X	X
Blood Sample for Chemistry Profile ^k	X ^k	X	X
CCI			
Blood Sample for Syphilis Testing (Local Laboratory)	X	X	X
Hepatitis B Testing (HBsAg/HBsAb/HBcAb)	X ^m		
Hepatitis C Testing (HCV Ab)	X ⁿ		
Estimated GFR	X ^o	X	X

Study Procedure	Open-Label Extension Treatment End of Week ^a		
	OL Week 96 and Every 12 Weeks until OL Week 408 ^b	30-Day Follow-up ^c	ESDD ^d
CCI			
Risk Reduction/Adherence Counseling	X		
Study Drug Dispensation and Accountability	X		X ^g
CD4, CD8, and CD4/CD8 cell count (for participants who acquire HIV)		X	X

Ab = antibody; Ag = antigen; BUN = blood urea nitrogen; CD4 = cluster determinant 4; CD8 = cluster determinant 8; DBS = dried blood spot; ESDD = early study drug discontinuation; HBcAb = hepatitis B core antibody; HBsAb = hepatitis B surface antibody; HBsAg = hepatitis B surface antigen; HCV = hepatitis C virus; OL = open label; PCR = polymerase chain reaction; STI = sexually transmitted infection

- a Visit windows are ± 14 days of the protocol-specified date, based on the end of blinded treatment phase visit, through the Open Label Extension phase visit, unless otherwise specified.
- b Participants will continue study visits in the OL extension phase every 12 weeks until OL Week 408.
- c Must be completed 30 days after discontinuing study drug. All participants who have received at least one dose of study drug will be required to complete a follow-up visit. For the purpose of scheduling a 30-Day Follow-Up visit, a ± 14 days window may be used.
- d Early Study Drug Discontinuation visit to occur within 72 hours of last dose of study drug.
- e Vital signs measurement including blood pressure, pulse, respiration rate, and temperature, every 24 weeks
- f Every 24 weeks
- g Swabs may be self-administered by the participant at the discretion of the investigator.
- h At a minimum, fourth generation rapid HIV-1 Ab/Ag or third generation rapid HIV-1 Ab test may be used. If fourth generation rapid HIV-1 Ag/Ab or third generation rapid HIV-1 Ab test is positive, retest will be completed. If rapid retest is positive, then HIV-1 RNA by PCR test and sample collection for possible genotypic testing will be completed.
- i If HIV-1 Ab/Ag is positive, then HIV-1 RNA by PCR test and sample collection for possible genotypic testing will be completed.
- j HIV-1 RNA by PCR and sample collection for possible genotypic resistance testing will be completed for any participants who (1) have a positive retest rapid HIV-1 Ab/Ag test or (2) have a positive HIV-1 Ab/Ag test or (3) show symptoms consistent with acute infection regardless of the results of the rapid tests, (4) have a recent exposure that is considered high risk for HIV infection, or (5) have been confirmed HIV-infected. If HIV infection is confirmed, participant will discontinue study drug immediately and should return for an ESDD visit within 72 hours. The participant will receive counseling and be referred for appropriate care. If viral load > 400 copies/mL the collected sample will be sent for genotypic resistance testing.
- k Chemistry profile: bicarbonate, BUN, calcium, chloride, creatinine, glucose, phosphorus, potassium, sodium **every 24 weeks.**
- l [REDACTED]
- m Hepatitis B testing (HBsAg, HBsAb, HBcAb) to be completed **every 48 weeks.**
- n Hepatitis C testing to be completed every 48 weeks.
- o Estimated GFR every **24 weeks**
- p [REDACTED]
- q No study drug dispensed.

Appendix 4. Management of Clinical and Laboratory Adverse Events

Appendix 5. Gilead Grading Scale for Severity of Adverse Events and Laboratory Abnormalities

Antiviral Toxicity Grading Scale Version: 01 April 2015

HEMATOLOGY				
	Grade 1	Grade 2	Grade 3	Grade 4
Hemoglobin HIV POSITIVE Adult and Pediatric ≥ 57 Days	8.5 to 10.0 g/dL 85 to 100 g/L	7.5 to < 8.5 g/dL 75 to < 85 g/L	6.5 to < 7.5 g/dL 65 to < 75 g/L	< 6.5 g/dL < 65 g/L
HIV NEGATIVE Adult and Pediatric ≥ 57 Days	10.0 to 10.9 g/dL 100 to 109 g/L OR Any decrease from Baseline 2.5 to < 3.5 g/dL 25 to < 35 g/L	9.0 to < 10.0 g/dL 90 to < 100 g/L OR Any decrease from Baseline 3.5 to < 4.5 g/dL 35 to < 45 g/L	7.0 to < 9.0 g/dL 70 to < 90 g/L OR Any decrease from Baseline ≥ 4.5 g/dL ≥ 45 g/L	< 7.0 g/dL < 70 g/L
Infant, 36–56 Days (HIV POSITIVE OR NEGATIVE)	8.5 to 9.4 g/dL 85 to 94 g/L	7.0 to < 8.5 g/dL 70 to < 85 g/L	6.0 to < 7.0 g/dL 60 to < 70 g/L	< 6.0 g/dL < 60 g/L
Infant, 22–35 Days (HIV POSITIVE OR NEGATIVE)	9.5 to 10.5 g/dL 95 to 105 g/L	8.0 to < 9.5 g/dL 80 to < 95 g/L	7.0 to < 8.0 g/dL 70 to < 80 g/L	< 7.0 g/dL < 70 g/L
Infant, 1–21 Days (HIV POSITIVE OR NEGATIVE)	12.0 to 13.0 g/dL 120 to 130 g/L	10.0 to < 12.0 g/dL 100 to < 120 g/L	9.0 to < 10.0 g/dL 90 to < 100 g/L	< 9.0 g/dL < 90 g/L
Absolute Neutrophil Count (ANC) Adult and Pediatric, ≥ 7 Months[#]	1000 to 1300/mm ³	750 to < 1000/mm ³	500 to < 750/mm ³	< 500/mm ³
	1.00 to 1.30 GI/L	0.75 to < 1.00 GI/L	0.50 to < 0.75 GI/L	< 0.50 GI/L
Absolute CD4+ Count HIV NEGATIVE ONLY Adult and Pediatric > 13 Years	300 to 400/mm ³ 300 to 400/μL	200 to < 300/mm ³ 200 to < 300/μL	100 to < 200/mm ³ 100 to < 200/μL	< 100/mm ³ < 100/μL

HEMATOLOGY				
	Grade 1	Grade 2	Grade 3	Grade 4
Absolute Lymphocyte Count HIV NEGATIVE ONLY Adult and Pediatric > 13 Years	600 to 650/mm ³ 0.60 to 0.65 GI/L	500 to < 600/mm ³ 0.50 to < 0.60 GI/L	350 to < 500/mm ³ 0.35 to < 0.50 GI/L	< 350/mm ³ < 0.35 GI/L
Platelets	100,000 to < 125,000/mm ³ 100 to < 125 GI/L	50,000 to < 100,000/mm ³ 50 to < 100 GI/L	25,000 to < 50,000/mm ³ 25 to < 50 GI/L	< 25,000/mm ³ < 25 GI/L
WBCs	2000/mm ³ to 2500/mm ³	1,500 to < 2,000/mm ³	1000 to < 1,500/mm ³	< 1000/mm ³
	2.00 GI/L to 2.50 GI/L	1.50 to < 2.00 GI/L	1.00 to < 1.50 GI/L	< 1.00 GI/L
Hypofibrinogenemia	100 to 200 mg/dL	75 to < 100 mg/dL	50 to < 75 mg/dL	< 50 mg/dL
	1.00 to 2.00 g/L	0.75 to < 1.00 g/L	0.50 to < 0.75 g/L	< 0.50 g/L
Hyperfibrinogenemia	> ULN to 600 mg/dL	> 600 mg/dL	—	—
	> ULN to 6.0 g/L	> 6.0 g/L	—	—
Fibrin Split Product	20 to 40 µg/mL	> 40 to 50 µg/mL	> 50 to 60 µg/mL	> 60 µg/mL
	20 to 40 mg/L	> 40 to 50 mg/L	> 50 to 60 mg/L	> 60 mg/L
Prothrombin Time (PT)	> 1.00 to 1.25 × ULN	> 1.25 to 1.50 × ULN	> 1.50 to 3.00 × ULN	> 3.00 × ULN
International Normalized Ratio of prothrombin time (INR)	1.1 to 1.5 × ULN	> 1.5 to 2.0 × ULN	> 2.0 to 3.0 × ULN	> 3.0 × ULN
Activated Partial Thromboplastin Time (APTT)	> 1.00 to 1.66 × ULN	> 1.66 to 2.33 × ULN	> 2.33 to 3.00 × ULN	> 3.00 × ULN
Methemoglobin	5.0 to 10.0%	> 10.0 to 15.0%	> 15.0 to 20.0%	> 20.0%

An overlap between the Grade 1 scale and the Lab's normal range for absolute neutrophils may result for pediatric participants. Please follow the Gilead convention of grading any result within the LLN and ULN a 0.

CHEMISTRY				
	Grade 1	Grade 2	Grade 3	Grade 4
Hyponatremia	130 to < LLN mEq/L	125 to < 130 mEq/L	121 to < 125 mEq/L	< 121 mEq/L
	130 to < LLN mmol/L	125 to < 130 mmol/L	121 to < 125 mmol/L	< 121 mmol/L
Hypernatremia	> ULN to 150 mEq/L	> 150 to 154 mEq/L	> 154 to 159 mEq/L	> 159 mEq/L
	> ULN to 150 mmol/L	> 150 to 154 mmol/L	> 154 to 159 mmol/L	> 159 mmol/L
Hypokalemia Adult and Pediatric ≥ 1 Year	3.0 to < LLN mEq/L	2.5 to < 3.0 mEq/L	2.0 to < 2.5 mEq/L	< 2.0 mEq/L
	3.0 to < LLN mmol/L	2.5 to < 3.0 mmol/L	2.0 to < 2.5 mmol/L	< 2.0 mmol/L
Infant <1 Year	3.0 to 3.4 mEq/L 3.0 to 3.4 mmol/L	2.5 to < 3.0 mEq/L 2.5 to < 3.0 mmol/L	2.0 to < 2.5 mEq/L 2.0 to < 2.5 mmol/L	< 2.0 mEq/L < 2.0 mmol/L
	Hyperkalemia Adult and Pediatric ≥ 1 Year	5.6 to 6.0 mEq/L 5.6 to 6.0 mmol/L	> 6.0 to 6.5 mEq/L > 6.0 to 6.5 mmol/L	> 6.5 to 7.0 mEq/L > 6.5 to 7.0 mmol/L
Infant <1 Year	> ULN to 6.0 mEq/L > ULN to 6.0 mmol/L	> 6.0 to 6.5 mEq/L > 6.0 to 6.5 mmol/L	> 6.5 to 7.0 mEq/L > 6.5 to 7.0 mmol/L	> 7.0 mEq/L > 7.0 mmol/L
	Hypoglycemia Adult and Pediatric ≥ 1 Month	55 to 64 mg/dL 3.03 to 3.58 mmol/L	40 to < 55 mg/dL 2.20 to < 3.03 mmol/L	30 to < 40 mg/dL 1.64 to < 2.20 mmol/L
Infant, < 1 Month		50 to 54 mg/dL 2.8 to 3.0 mmol/L	40 to < 50 mg/dL 2.2 to < 2.8 mmol/L	30 to < 40 mg/dL 1.7 to < 2.2 mmol/L
	Hyperglycemia, Nonfasting	116 to 160 mg/dL	> 160 to 250 mg/dL	> 250 to 500 mg/dL
6.42 to 8.91 mmol/L		> 8.91 to 13.90 mmol/L	> 13.90 to 27.79 mmol/L	> 27.79 mmol/L
Hyperglycemia, Fasting	110 to 125 mg/dL 6.08 to 6.96 mmol/L	> 125 to 250 mg/dL > 6.96 to 13.90 mmol/L	> 250 to 500 mg/dL > 13.90 to 27.79 mmol/L	> 500 mg/dL > 27.79 mmol/L

CHEMISTRY				
	Grade 1	Grade 2	Grade 3	Grade 4
Hypocalcemia (corrected for albumin if appropriate*) Adult and Pediatric ≥ 2 Years	7.8 < LLN mg/dL 1.94 to < LLN mmol/L	7.0 to < 7.8 mg/dL 1.74 to < 1.94 mmol/L	6.1 to < 7.0 mg/dL 1.51 to < 1.74 mmol/L	< 6.1 mg/dL < 1.51 mmol/L
Pediatric ≥ 7 days - 2 Years	7.8 to 8.4 mg/dL 1.94 to 2.10 mmol/L	7.0 to < 7.8 mg/dL 1.74 to < 1.94 mmol/L	6.1 to < 7.0 mg/dL 1.51 to < 1.74 mmol/L	< 6.1 mg/dL < 1.51 mmol/L
Infant, < 7 Days	6.5 to 7.5 mg/dL 1.61 to 1.88 mmol/L	6.0 to < 6.5 mg/dL 1.49 to < 1.61 mmol/L	5.5 to < 6.0 mg/dL 1.36 to < 1.49 mmol/L	< 5.5 mg/dL < 1.36 mmol/L
Hypercalcemia (corrected for albumin if appropriate*) Adult and Pediatric ≥ 7 Days	> ULN to 11.5 mg/dL	> 11.5 to 12.5 mg/dL	> 12.5 to 13.5 mg/dL	> 13.5 mg/dL
	> ULN to 2.88 mmol/L	> 2.88 to 3.13 mmol/L	> 3.13 to 3.38 mmol/L	> 3.38 mmol/L
Infant, < 7 Days	11.5 to 12.4 mg/dL 2.86 to 3.10 mmol/L	> 12.4 to 12.9 mg/dL > 3.10 to 3.23 mmol/L	> 12.9 to 13.5 mg/dL > 3.23 to 3.38 mmol/L	> 13.5 mg/dL > 3.38 mmol/L
Hypocalcemia (ionized)	3.0 mg/dL to < LLN	2.5 to < 3.0 mg/dL	2.0 to < 2.5 mg/dL	< 2.0 mg/dL
	0.74 mmol/L to < LLN	0.62 to < 0.74 mmol/L	0.49 to < 0.62 mmol/L	< 0.49 mmol/L
Hypercalcemia (ionized)	> ULN to 6.0 mg/dL	> 6.0 to 6.5 mg/dL	> 6.5 to 7.0 mg/dL	> 7.0 mg/dL
	> ULN to 1.50 mmol/L	> 1.50 to 1.63 mmol/L	> 1.63 to 1.75 mmol/L	> 1.75 mmol/L
Hypomagnesemia	1.40 to < LLN mg/dL 1.2 to < LLN mEq/L	1.04 to < 1.40 mg/dL 0.9 to < 1.2 mEq/L	0.67 to < 1.04 mg/dL 0.6 to < 0.9 mEq/L	< 0.67 mg/dL < 0.6 mEq/L
	0.58 to < LLN mmol/L	0.43 to < 0.58 mmol/L	0.28 to < 0.43 mmol/L	< 0.28 mmol/L
Hypophosphatemia Adult and Pediatric > 14 Years	2.0 to < LLN mg/dL 0.63 to < LLN mmol/L	1.5 to < 2.0 mg/dL 0.47 to < 0.63 mmol/L	1.0 to < 1.5 mg/dL 0.31 to < 0.47 mmol/L	< 1.0 mg/dL < 0.31 mmol/L

CHEMISTRY				
	Grade 1	Grade 2	Grade 3	Grade 4
Pediatric 1 Year–14 Years	3.0 to < LLN mg/dL 0.96 to < LLN mmol/L	2.5 to < 3.0 mg/dL 0.80 to < 0.96 mmol/L	1.5 to < 2.5 mg/dL 0.47 to < 0.80 mmol/L	< 1.5 mg/dL < 0.47 mmol/L
Pediatric < 1 Year	3.5 to < LLN mg/dL 1.12 to < LLN mmol/L	2.5 to < 3.5 mg/dL 0.80 to < 1.12 mmol/L	1.5 to < 2.5 mg/dL 0.47 to < 0.80 mmol/L	< 1.5 mg/dL < 0.47 mmol/L
Hyperbilirubinemia Adult and Pediatric > 14 Days	> 1.0 to 1.5 × ULN	> 1.5 to 2.5 × ULN	> 2.5 to 5.0 × ULN	> 5.0 × ULN
Infant, ≤ 14 Days (non-hemolytic)	NA	20.0 to 25.0 mg/dL 342 to 428 μmol/L	> 25.0 to 30.0 mg/dL > 428 to 513 μmol/L	> 30.0 mg/dL > 513 μmol/L
Infant, ≤ 14 Days (hemolytic)	NA	NA	20.0 to 25.0 mg/dL 342 to 428 μmol/L	> 25.0 mg/dL > 428 μmol/L
Blood Urea Nitrogen	1.25 to 2.50 × ULN	> 2.50 to 5.00 × ULN	> 5.00 to 10.00 × ULN	> 10.00 × ULN
Hyperuricemia	> ULN to 10.0 mg/dL	> 10.0 to 12.0 mg/dL	> 12.0 to 15.0 mg/dL	> 15.0 mg/dL
	> ULN to 597 μmol/L	> 597 to 716 μmol/L	> 716 to 895 μmol/L	> 895 μmol/L
Hypouricemia Adult and Pediatric ≥ 1 year	1.5 mg/dL to < LLN 87 μmol/L to < LLN	1.0 to < 1.5 mg/dL 57 to < 87 μmol/L	0.5 to < 1.0 mg/dL 27 to < 57 μmol/L	< 0.5 mg/dL < 27 μmol/L
	N/A	1.0 mg/dL to < LLN- 57 μmol to < LLN	0.5 to < 1.0 mg/dL 27 to < 57 μmol/L	< 0.5 mg/dL < 27 μmol/L
Creatinine**	> 1.50 to 2.00 mg/dL > 133 to 177 μmol/L	> 2.00 to 3.00 mg/dL > 177 to 265 μmol/L	> 3.00 to 6.00 mg/dL > 265 to 530 μmol/L	> 6.00 mg/dL > 530 μmol/L
Bicarbonate Adult and Pediatric ≥ 4 Years	16.0 mEq/L to < LLN	11.0 to < 16.0 mEq/L	8.0 to < 11.0 mEq/L	< 8.0 mEq/L
	16.0 mmol/L to < LLN	11.0 to < 16.0 mmol/L	8.0 to < 11.0 mmol/L	< 8.0 mmol/L
Pediatric < 4 Years	NA	11.0 mEq/L to < LLN	8.0 to < 11.0 mEq/L	< 8.0 mEq/L
		11.0 mmol/L to < LLN	8.0 to < 11.0 mmol/L	< 8.0 mmol/L

CHEMISTRY

	Grade 1	Grade 2	Grade 3	Grade 4
Triglycerides (Fasting)	NA	500 to 750 mg/dL 5.64–8.47 mmol/L	> 750 to 1200 mg/dL > 8.47–13.55 mmol/L	> 1200 mg/dL > 13.55 mmol/L
LDL (Fasting) Adult	130 to 160 mg/dL	>160 to 190 mg/dL	> 190 mg/dL	NA
	3.35 to 4.15 mmol/L	> 4.15 to 4.92 mmol/L	> 4.92 mmol/L	
LDL (Fasting) Pediatric >2 to <18 years	110 to 130 mg/dL	> 130 to 190 mg/dL	> 190 mg/dL	NA
	2.84 to 3.37 mmol/L	> 3.37 to 4.92 mmol/L	> 4.92 mmol/L	
Hypercholesterolemia (Fasting)	200 to 239 mg/dL	> 239 to 300 mg/dL	> 300 mg/dL	NA
	5.16 to 6.19 mmol/L	> 6.19 to 7.77 mmol/L	> 7.77 mmol/L	
Pediatric < 18 Years	170 to 199 mg/dL 4.39 to 5.15 mmol/L	> 199 to 300 mg/dL > 5.15 to 7.77 mmol/L	> 300 mg/dL > 7.77 mmol/L	NA
Creatine Kinase	3.0 to < 6.0 × ULN	6.0 to < 10.0 × ULN	10.0 to < 20.0 × ULN	≥ 20.0 × ULN

* Calcium should be corrected for albumin if albumin is < 4.0 g/dL

** An overlap between the Grade 1 scale and the Lab's normal range for creatinine may result for Male participants > 70 yrs. Please follow the Gilead convention of grading any result within the LLN and ULN a 0.

ENZYMES

	Grade 1	Grade 2	Grade 3	Grade 4
AST (SGOT)	1.25 to 2.50 × ULN	> 2.50 to 5.00 × ULN	> 5.00 to 10.00 × ULN	> 10.00 × ULN
ALT (SGPT)	1.25 to 2.50 × ULN	> 2.50 to 5.00 × ULN	> 5.00 to 10.00 × ULN	> 10.00 × ULN
GGT	1.25 to 2.50 × ULN	> 2.50 to 5.00 × ULN	> 5.00 to 10.00 × ULN	> 10.00 × ULN
Alkaline Phosphatase	1.25 to 2.50 × ULN	> 2.50 to 5.00 × ULN	> 5.00 to 10.00 × ULN	> 10.00 × ULN
Total Amylase	> 1.0 to 1.5 × ULN	> 1.5 to 2.0 × ULN	> 2.0 to 5.0 × ULN	> 5.0 × ULN
Pancreatic Amylase	> 1.0 to 1.5 × ULN	> 1.5 to 2.0 × ULN	> 2.0 to 5.0 × ULN	> 5.0 × ULN
Lipase	> 1.0 to 1.5 × ULN	> 1.5 to 3.0 × ULN	> 3.0 to 5.0 × ULN	> 5.0 × ULN
Albumin Pediatrics <16 years	-	2.0 to < LLN g/dL 20 to < LLN g/L	< 2.0 g/dL < 20 g/L	NA
≥ 16 years	3.0 g/dL to < LLN 30 g/L to < LLN	2.0 to < 3.0 g/dL 20 to < 30 g/L	< 2.0 g/dL < 20 g/L	NA

URINALYSIS

	Grade 1	Grade 2	Grade 3	Grade 4
Hematuria (Dipstick)	1+	2+	3-4+	NA
Hematuria (Quantitative) See Note below				
Females	> ULN - 10 RBC/HPF	> 10-75 RBC/HPF	> 75 RBC/HPF	NA
Males	6-10 RBC/HPF	> 10-75 RBC/HPF	> 75 RBC/HPF	NA
Proteinuria (Dipstick)	1+	2-3+	4+	NA
Proteinuria, 24 Hour Collection				
Adult and Pediatric ≥ 10 Years	200 to 999 mg/24 h	> 999 to 1999 mg/24 h	> 1999 to 3500 mg/24 h	> 3500 mg/24 h
Pediatric > 3 Mo to < 10 Years	201 to 499 mg/m ² /24 h	> 499 to 799 mg/m ² /24 h	> 799 to 1000 mg/m ² /24 h	> 1000 mg/m ² /24 h
Glycosuria (Dipstick)	1+	2-3+	4+	NA

Notes:

- Toxicity grades for Quantitative and Dipstick Hematuria will be assigned by the central laboratory (Prior to OL Week 96); however, for other laboratories, toxicity grades will only be assigned to Dipstick Hematuria.
- With the exception of lipid tests, any graded laboratory test with a result that is between the LLN and ULN should be assigned Grade 0.
- If the severity of a clinical AE could fall under either one of two grades (eg, the severity of an AE could be either Grade 2 or Grade 3), select the higher of the two grades for the AE.

CARDIOVASCULAR				
	Grade 1	Grade 2	Grade 3	Grade 4
Cardiac Arrhythmia (general) (By ECG or physical exam)	Asymptomatic AND No intervention indicated	Asymptomatic AND Non-urgent medical intervention indicated	Symptomatic, non-life-threatening AND Non-urgent medical intervention indicated	Life-threatening arrhythmia OR Urgent intervention indicated
Cardiac-ischemia/Infarction	NA	NA	Symptomatic ischemia (stable angina) OR Testing consistent with ischemia	Unstable angina OR Acute myocardial infarction
Hemorrhage (significant acute blood loss)	NA	Symptomatic AND No transfusion indicated	Symptomatic AND Transfusion of ≤ 2 units packed RBCs (for children ≤ 10 cc/kg) indicated	Life-threatening hypotension OR Transfusion of > 2 units packed RBCs indicated (for children ≤ 10 cc/kg) indicated
Hypertension (with repeat testing at same visit)	140–159 mmHg systolic OR 90–99 mmHg diastolic	> 159–179 mmHg systolic OR > 99–109 mmHg diastolic	> 179 mmHg systolic OR > 109 mmHg diastolic	Life-threatening consequences (eg, malignant hypertension) OR Hospitalization (other than ER visit) indicated
Pediatric ≤ 17 Years (with repeat testing at same visit)	NA	91st–94th percentile adjusted for age, height, and gender (systolic and/or diastolic)	≥ 95th percentile adjusted for age, height, and gender (systolic and/or diastolic)	Life-threatening consequences (eg, malignant hypertension) OR Hospitalization indicated (other than emergency room visit)
Hypotension	NA	Symptomatic, corrected with oral fluid replacement	Symptomatic, IV fluids indicated	Shock requiring use of vasopressors or mechanical assistance to maintain blood pressure
Pericardial Effusion	Asymptomatic, small effusion requiring no intervention	Asymptomatic, moderate or larger effusion requiring no intervention	Effusion with non-life-threatening physiologic consequences OR Effusion	Life-threatening consequences (eg, tamponade) OR Urgent intervention indicated

CARDIOVASCULAR				
	Grade 1	Grade 2	Grade 3	Grade 4
			with nonurgent intervention indicated	
Prolonged PR Interval	PR interval 0.21 to 0.25 sec	PR interval > 0.25 sec	Type II 2nd degree AV block OR Ventricular pause > 3.0 sec	Complete AV block
Pediatric ≤ 16 Years	1st degree AV block (PR > normal for age and rate)	Type I 2nd degree AV block	Type II 2nd degree AV block	Complete AV block
Prolonged QTc	Asymptomatic, QTc interval 0.45 to 0.47 sec OR Increase interval < 0.03 sec above baseline	Asymptomatic, QTc interval 0.48 to 0.49 sec OR Increase in interval 0.03 to 0.05 sec above baseline	Asymptomatic, QTc interval ≥ 0.50 sec OR Increase in interval ≥ 0.06 sec above baseline	Life-threatening consequences, eg, Torsade de pointes or other associated serious ventricular dysrhythmia
Pediatric ≤ 16 Years	Asymptomatic, QTc interval 0.450 to 0.464 sec	Asymptomatic, QTc interval 0.465 to 0.479 sec	Asymptomatic, QTc interval ≥ 0.480 sec	Life-threatening consequences, eg, Torsade de pointes or other associated serious ventricular dysrhythmia
Thrombosis/Embolism	NA	Deep vein thrombosis AND No intervention indicated (eg, anticoagulation, lysis filter, invasive procedure)	Deep vein thrombosis AND Intervention indicated (eg, anticoagulation, lysis filter, invasive procedure)	Embolic event (eg, pulmonary embolism, life-threatening thrombus)
Vasovagal Episode (associated with a procedure of any kind)	Present without loss of consciousness	Present with transient loss of consciousness	NA	NA
Ventricular Dysfunction (congestive heart failure, CHF)	NA	Asymptomatic diagnostic finding AND intervention indicated	New onset with symptoms OR Worsening symptomatic CHF	Life-threatening CHF

RESPIRATORY

	Grade 1	Grade 2	Grade 3	Grade 4
Bronchospasm (acute)	FEV1 or peak flow reduced to 70% to 80%	FEV1 or peak flow 50% to 69%	FEV1 or peak flow 25% to 49%	Cyanosis OR FEV1 or peak flow < 25% OR Intubation
Dyspnea or Respiratory Distress	Dyspnea on exertion with no or minimal interference with usual social & functional activities	Dyspnea on exertion causing greater than minimal interference with usual social & functional activities	Dyspnea at rest causing inability to perform usual social & functional activities	Respiratory failure with ventilatory support indicated
Pediatric < 14 Years	Wheezing OR minimal increase in respiratory rate for age	Nasal flaring OR Intercostal retractions OR Pulse oximetry 90% to 95%	Dyspnea at rest causing inability to perform usual social & functional activities OR Pulse oximetry < 90%	Respiratory failure with ventilatory support indicated

OCULAR/VISUAL

	Grade 1	Grade 2	Grade 3	Grade 4
Uveitis	Asymptomatic but detectable on exam	Symptomatic anterior uveitis OR Medical intervention indicated	Posterior or pan-uveitis OR Operative intervention indicated	Disabling visual loss in affected eye(s)
Visual Changes (from baseline)	Visual changes causing no or minimal interference with usual social & functional activities	Visual changes causing greater than minimal interference with usual social & functional activities	Visual changes causing inability to perform usual social & functional activities	Disabling visual loss in affected eye(s)

SKIN				
	Grade 1	Grade 2	Grade 3	Grade 4
Alopecia	Thinning detectable by study participant or caregiver (for disabled adults)	Thinning or patchy hair loss detectable by health care provider	Complete hair loss	NA
